7.2 Sample Size and Accrual

We originally anticipated 100-150 patients to be enrolled per year. A sample size of 66 in each group will have 80% power to detect a difference in mean EORTC scores of 10.000 assuming that the common standard deviation is 22.900 using two group t-test with a 0.050 one-sided significance level. The target sample size was 140 patients to allow appropriate block randomization in groups of 20. Based on enrolling about 140 patients, we would be powered to detect an effect size of 0.437 (difference in means of 10, common standard deviation of 22.9). Due to slower accrual in context of COVID-19, we anticipate enrollment of 100-140 patients before funding ends. With 100 patients, we will have 80% power to detect an effect size of 0.501 (difference in means of 11.467, common standard deviation of 22.9). Power calculations were performed using SAS version 9.4 (SAS Inc., Cary, NC) using PROC POWER and a two sample means difference test.

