7.3 Data Analysis Plans

7.3.1 Aim 1: Impact of PRO monitoring with symptom alerts, compared to PRO monitoring without alerts, after thoracic surgery on post-operative quality of life.

Impact will be determined by comparing baseline quality of life to quality of life at the following timepoints: Day 14, Day 60, Day 120, Day 180, and Day 365 post-discharge. QOL will be measured by administering European Organisation for Research and Treatment of Cancer's (EORTC) EORTC QLQ-LC13 and EORTC QLQ-C30. These surveys will be scored according to methods described in the EORTC scoring manual: <https://qol.eortc.org/manual/scoring-manual>.

Student's T and/or Wilcoxon rank sum tests will be used to perform bivariable comparisons of EORTC scores at each of the time points (baseline/pre-operative and Day 12, Day 60, Day 120, Day 180, and Day 365 post-operative).

Additionally, a linear mixed effect model will be used to assess the average

change in EORTC scores over time amongst both groups, and the difference in average trajectory between them, after accounting for repeated measures and within- and between- subject variability. Both a random intercept and slope (for time) statement will be used, and an unstructured correlation matrix will be applied. The random intercept and slope will allow us to assess the impact of symptom alerts while allowing for random variation in baseline quality of life and trajectories.

If there are convergence issues, simpler correlation structures may be used (e.g. independent) or the random slope parameter may be dropped. Dropping the random slope parameter will mean we are assuming that there is no/minimal individual variation in trajectory across patients.

7.3.2 Aim 2: Determine feasibility of 3-month post-operative PRO symptom monitoring with alerts.

The proportion of completed symptom surveys (overall and in each arm) at 3-months postoperative will be calculated, as well as the proportion of participants who completed all surveys during that time. Chi-square, Student's T, and Wilcoxon rank sum tests will be used to compare patient demographics, study arm, and surgery characteristics between those who did and did not complete all surveys to attempt to identify predictors of compliance. Multivariable logistic regression may also be used.

Similar methods will be used to assess proportion of symptom alerts that generate a clinician response.

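### Section 7.2 powers a single t-test on an unnamed EORTC score with every enrolled patient measured, while section 7.3.1 does not say which quality-of-life analysis decides Aim 1

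*Combined protocol and SAP*

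**What the plan says.** Section 2.1 of the combined protocol and SAP lists three primary objectives. The first is the effect of alerts on post-operative quality of life, and it is the only objective with a power statement.

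- **Section 7.2, test and size:** "A sample size of 66 in each group will have 80% power to detect a difference in mean EORTC scores of 10.000", with a standard deviation of 22.9, "using two group t-test with a 0.050 one-sided significance level". No EORTC score and no visit is named.
- **Section 7.2, enrolment:** "The target sample size was 140 patients to allow appropriate block randomization in groups of 20". After slower accrual the expected range is 100 to 140, and "With 100 patients, we will have 80% power to detect an effect size of 0.501", given as a difference of 11.467. No rate of missing scores appears.
- **Section 7.3.1, visits:** "Impact will be determined by comparing baseline quality of life to quality of life at the following timepoints", namely "Day 14, Day 60, Day 120, Day 180, and Day 365 post-discharge". The instruments are the QLQ-C30 and the QLQ-LC13.
- **Section 7.3.1, tests:** Student's t "and/or Wilcoxon rank sum tests will be used to perform bivariable comparisons of EORTC scores at each of the time points". A linear mixed model for the difference in average trajectory between arms is then added. None of these is called primary, and no level or multiplicity rule is given. This sentence lists the follow-up visits as "Day 12, Day 60, Day 120, Day 180, and Day 365 post-operative".
- **Section 4.2:** some patients are expected to stop study procedures early, and analysis of participant data is to run throughout the four years.

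**The concern.** An error rate and a power belong to one specified comparison. Section 7.2 gives both for one t-test, but section 7.3.1 offers several scores, five follow-up visits, a choice between two tests at each visit, and a model. A reader of the final report could not tell which of these had been expected to show the effect. If the visit tests decide, the error rate depends on a rule that the plan does not state. If the mixed model decides, section 7.2 gives no power for it.

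The second strand is the number of patients with a score. If the deciding result is a t-test at one visit, only patients with a score at that visit contribute. At 100 enrolled, the 80% figure holds only if all 100 have one.

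**Working it through.** **Inputs.** From section 7.2: difference 10 (11.467 for 100 patients), SD 22.9, one-sided level 0.05, two-group t-test, 66 per arm, 140 or 100 enrolled. From section 7.1: 1:1 allocation. From section 7.3.1: five follow-up visits. Assumed, because the documents give no figures: 10, 20 and 30% missing scores at the tested visit, equal in both arms, and correlations of 0.5 to 0.9 between visits.

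**Step 1. Reproduce the plan's figures.** With n per arm, the noncentrality is difference / (22.9 × √(2/n)) on 2n − 2 degrees of freedom. Power is the chance that a noncentral t exceeds the one-sided 5% critical value.

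- 66 per arm, 10 points: 10 / (22.9 × √(2/66)) = 2.51; critical value 1.657; power 80.2%. The plan's 66 is right.
- 50 per arm, 11.467 points: noncentrality 2.50; critical value 1.661; power 80.0%. The plan's 100-patient figure is right.
- 70 per arm, 10 points: noncentrality 2.58; power 82.3%. The effect size of 0.437 quoted for 140 patients is 10/22.9, the effect used to size 66 per arm.

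**Step 2. Slack for missing scores.** 1 − 132/140 = 5.7%. At 100 enrolled the calculation already uses all 50 per arm, so the slack is zero.

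**Step 3. Power of a single-visit t-test with missing scores.** Same formula, with n multiplied by (1 − missing rate). The detectable difference is at 80% power.

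| Enrolled | Assumed missing | Scores per arm | Difference tested | Power | Detectable difference |
|---|---|---|---|---|---|
| 140 | 10% | 63 | 10 | 79% | 10.2 |
| 140 | 20% | 56 | 10 | 74% | 10.8 |
| 140 | 30% | 49 | 10 | 69% | 11.6 |
| 100 | 10% | 45 | 11.467 | 76% | 12.1 |
| 100 | 20% | 40 | 11.467 | 72% | 12.8 |
| 100 | 30% | 35 | 11.467 | 67% | 13.7 |

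**Step 4. Illustration of why a deciding rule is needed.** Suppose that one favourable t-test at any of the five visits, on one score, counted as impact. The false-positive chance is then the probability that the largest of five correlated standard normal statistics exceeds 1.645. Simulation with 400,000 draws and equal correlation between visits gives 16.6% at correlation 0.5, 13.5% at 0.7 and 9.4% at 0.9, against a nominal 5%. The plan neither states nor excludes this rule.

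**The case against.** The strongest reply is that this is a self-described feasibility study, with quality of life as one of three primary objectives. Section 7.3.1 does describe between-arm contrasts. Its heading compares monitoring with and without alerts, and the mixed model is specified in detail and linked to assessing the impact of alerts, so the visit tests could be read as descriptive. The mixed model can also use partial data, and the late windows in section 4.3 may limit missing visits.

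Much of this stands and limits the severity. It does not remove the point: the model is introduced as an addition and is never called primary, and if it is primary, the power in section 7.2 belongs to a different test.

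Some stronger readings are tempting, but the documents do not support them:

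- **Aim 1 has a 9–17% false-positive rate.** That needs an any-visit rule that the plan does not contain, and correlations that it does not give.
- **Sidedness is undefined, or the test is really two-sided.** Section 7.2 states one-sided 0.05. Section 7.3.1 is only silent, and nothing points to a two-sided test.
- **Half the scores are expected to be missing.** The 50% figure in section 2.2 is a feasibility threshold for completing every quality-of-life survey, not a forecast for one visit.
- **Between-arm results have been seen.** The sentence on continuing analysis in section 4.2 is general and may refer to the interviews, which section 7.3.3 says are analysed as they are collected.
- **Day 12 is a separate visit.** The other four days match the preceding sentence, and section 4.3 schedules the EORTC surveys at Day 14 post-discharge, so it is probably a slip.

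**Conclusion.** The point holds and should be fixed, but given the study's feasibility character it is not a must-fix defect. The arithmetic in section 7.2 is correct. What is missing is the link between that calculation and a deciding analysis in section 7.3.1; without it, the 5% error and 80% power do not describe the Aim 1 conclusion. This part rests on the text alone.

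The missing-score part is conditional. For a single-visit t-test, any missing score at 100 enrolled, or more than 5.7% missing at 140, takes power below the stated 80%. How far below depends on the assumed rates: down to 69% (140 enrolled) or 67% (100 enrolled) at 30% missing. These losses need not apply to a mixed-model contrast, for which the plan gives no power.

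**What to change.** **Section 7.3.1.** Name one primary score, for example QLQ-C30 global health status/QoL, which fits the references to global QOL in sections 1.3 and 4.1. Name one deciding between-arm contrast: either one visit with one test, or one mixed-model contrast. Say whether it is on the score or on change from baseline. Carry over the one-sided 0.05 level from section 7.2, and label all other scores, visits and tests supportive. Make and date this choice without sight of between-arm quality-of-life results. If that cannot be shown, label the comparison exploratory. As an editorial item, bring the Day 12 post-operative wording into line with the Day 14 post-discharge schedule.

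**Section 7.2.** Restate power or detectable difference for the chosen contrast at a stated missing rate. For a single-visit t-test this could read: 100 enrolled, 20% missing, 40 per arm, detectable difference 12.8 points. For a mixed-model contrast, give power under stated correlation and missingness assumptions.

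**Cost.** A text amendment, a new power calculation if the mixed model is chosen, and a less favourable stated power if a single-visit t-test is chosen. Other comparisons become supportive. No extra enrolment is needed.

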3.2 Exclusion Criteria

All patients meeting any of the following exclusion criteria at baseline will be excluded from study participation:

- 3.2.1 Not completing planned surgery within 3 months of obtaining informed consent
- 3.2.2 Diagnosis of esophageal cancer
- 3.2.3 Inability to read and speak English
- 3.2.4 Presenting for day surgery
- 3.2.5 Presenting for foregut surgery (e.g. paraesophageal hernia repair)
- 3.2.6 Dementia, altered mental status, or any psychiatric condition that would prohibit the understanding or rendering of informed consent.
- 3.2.7 Current incarceration
- 3.2.8 Pregnancy

Caregivers meeting any of the following exclusion criteria at baseline will be excluded from study participation:

[figure not shown]
- 3.2.9 Inability to read and speak English

- 3.2.10 Dementia, altered mental status, or any psychiatric condition that would prohibit the understanding or rendering of informed consent.
- 3.2.11 Current incarceration
- 3.2.12 Not currently providing care for a patient who has undergone thoracic surgery and enrolled in the PRO portion of the study
- 3.2.13 Receiving extensive medical treatment (e.g., caregivers admitted in the intensive care unit)

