4.2 Duration of Study

This study will last for approximately 4 years. Up to a total of 140 participants will be enrolled over two years. A subset of approximately 40 patients with varying postoperative experiences and their caregivers will also participate in a semi-structured interview for a total accrual goal of 180 participants. Each patients' participation in the study will last up to 2 years and 3 months. Some patients will have a shortened participation period due to early discontinuation of study procedures. Study analysis of participant data will take place throughout the 4 years.

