4.5 Removal of Patients from Protocol

Patients will be removed from the study if:

- they experience significant emotional distress in response to PRO surveys
- they indicate that they no longer wish to participate

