7.3.3 Aim 3: Identify barriers/facilitators of PRO monitoring through semi-structured interviews.

Patient and caregiver interview transcripts will be analyzed as they are collected. Transcripts will be coded using in vivo coding methods and a code book will be created. Interviews will continue until thematic saturation is achieved, which will be defined by no new codes being generated to add to the code book.

7.3.4 Sub-Aim 1: Impact of PRO monitoring with symptom alerts, compared to PRO monitoring without symptom alerts, on post-operative readmission and mortality rates.

Kaplan Meier curves and Cox proportional hazards regression will be used to assess the impact of study treatment arm on 30-day and 90-day emergency department (ED) visits, readmissions, and all-cause mortality, as well as 1-year all-cause mortality. A linear mixed effect model will be used to assess the change in 2-year quality of life (described in Aim 1).

Patients who are lost to follow-up will be censored at their last clinician/study interaction. Mortality will be treated as a competing risk for ED visits and readmission. This aim will be approached as an intent-to-treat analysis and will not require that patients used their PRO monitoring or had symptom alerts sent to

their clinician.

7.3.5 Sub-Aim 2: Determine the feasibility of PRO monitoring for assessing quality of life.

Similar methods to Aim 2 will be used. The proportion of completed QOL surveys (overall and in each arm) at each time point (baseline/pre-operative and 2-weeks, 6-months, 1-year, and 2-year post-operative) will be calculated, as well as the proportion of participants who completed all surveys during that time. Chi-square, Student's T, and Wilcoxon rank sum tests will be used to compare patient demographics, study arm, and surgery characteristics between those who did and did not complete all surveys to attempt to identify predictors of compliance. Multivariable logistic regression may also be used.

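### The 80% power stated for 100 patients holds only if all 50 per arm have the analysed EORTC score; section 7.2 allows for no loss, although the protocol foresees it

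*Combined protocol and SAP*

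**What the plan says.** Section 7.2 starts from 66 per group: 80% power for a 10-point difference in mean EORTC score, SD 22.9, "using two group t-test with a 0.050 one-sided significance level". It then explains the step from 132 to 140: "The target sample size was 140 patients to allow appropriate block randomization in groups of 20". Because accrual slowed, it now anticipates enrolling 100-140 and adds: "With 100 patients, we will have 80% power to detect an effect size of 0.501", equated to 11.467 points at the same SD. It mentions no dropout, no missing scores and no evaluable number.

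Section 7.3.1 (Aim 1, a primary objective) plans this: "Student's T and/or Wilcoxon rank sum tests will be used to perform bivariable comparisons of EORTC scores at each of the time points", out to Day 365. It adds a linear mixed model with random intercept and slope.

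Elsewhere the protocol expects some patients to have no score at a given time point:

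- Section 3.2.1 excludes for "Not completing planned surgery within 3 months of obtaining informed consent", while the table in 5.1 places randomization at baseline.
- Section 4.2: "Some patients will have a shortened participation period due to early discontinuation of study procedures".
- Section 4.5 removes patients if "they indicate that they no longer wish to participate", or if the surveys cause significant distress.
- Section 7.3.4: "Patients who are lost to follow-up will be censored at their last clinician/study interaction". Mortality is itself an outcome (2.2.1).
- Section 2.2.2 counts long-term quality-of-life monitoring as feasible if at least half of the patients complete every QOL survey.

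**The concern.** The power figures use the number enrolled as if it were the number analysed. A t or Wilcoxon test at one time point uses only patients with a score at that time point, so any loss lowers power below the stated value. The 100-patient scenario has no margin at all. The 140-patient scenario has a small one, which 7.2 attributes to block size and not to loss.

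If the trial closes near 100 patients and the quality-of-life comparison is not significant, readers will judge it against 80% power for about 11.5 points. With loss, the trial would have had less power than that, and the result would seem to rule out more than it does.

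**Working it through.** **Inputs.** From 7.2: SD 22.9; one-sided α = 0.05; differences of 10 and 11.467 points; 100 or 140 enrolled. From 7.1: 1:1 allocation, hence 50 or 70 per arm. Loss rates are assumed, because the documents give none.

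**Formula.** For n analysed per arm and difference Δ, the noncentrality is λ = (Δ/22.9)·√(n/2), with 2n − 2 degrees of freedom. Power is P(T′ > t₀.₉₅), where T′ is noncentral t with parameter λ. The difference detectable with 80% power is the Δ that solves power = 0.80.

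**Step 1: reproduce the plan's figures.**

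- n = 50, Δ = 11.467: λ = 0.5007 × √25 = 2.504; critical t (98 df) = 1.661; power 80.0%. The 80%-power difference at n = 50 is 11.47. Both match 7.2, so all 100 patients are counted as analysed.
- n = 66, Δ = 10: power 80.25%. At n = 65 it is 79.7%, so 66 is the smallest sufficient number.
- Two-sided 0.05 at n = 50 gives 69.8% for 11.467 points, so the stated figures are one-sided.

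**Step 2: margin.** At 100 enrolled, one missing score per arm (n = 49) gives 79.3%. At 47 per arm (6% loss) power is 77.8%, more than 2 points short. At 140 enrolled, 132 must be analysed, so the tolerated loss is 1 − 132/140 = 5.7%.

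**Step 3: apply assumed loss,** n = enrolled per arm × (1 − loss), rounded.

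| Loss | 100 enrolled: n/arm | Power for 11.467 | 80%-power difference | Power for 10 | 140 enrolled: n/arm | Power for 10 | 80%-power difference |
|---|---|---|---|---|---|---|---|
| 0% | 50 | 80.0% | 11.5 | 70.0% | 70 | 82.3% | 9.7 |
| 8% | 46 | 77.0% | 12.0 | 66.8% | 64 | 79.2% | 10.1 |
| 10% | 45 | 76.2% | 12.1 | 65.9% | 63 | 78.6% | 10.2 |
| 20% | 40 | 71.7% | 12.8 | 61.5% | 56 | 74.3% | 10.8 |
| 30% | 35 | 66.6% | 13.7 | 56.5% | 49 | 69.2% | 11.6 |

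The 8% row is illustrative. If exactly 50% completed all 8 QOL surveys (Figure 2 in 4.3) and misses were independent, completion per time point would be 0.5^(1/8) = 0.917, which is about 46 of 50 and 64 of 70 per arm.

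**The case against.** The strongest reply is that nothing in 7.2 is miscalculated and that every loss figure above is assumed. That is true. The fault is the number to which a correct calculation is applied, and the size of the shortfall is a range and not an estimate. At 5% loss (48 per arm) power is still 78.5%, and at 140 enrolled a loss of 8-10% leaves 79%. The point is material mainly near 100 patients.

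The evidence for loss is uneven. The 50% feasibility threshold is a minimum for success and not a forecast, and it covers surveys at Days 545 and 730, beyond Aim 1. The shortened participation in 4.2 could fall after Day 365. The censoring rule in 7.3.4 belongs to the time-to-event analyses. Wide survey windows, staff help and paper backup should limit missing scores. Patients excluded under 3.2.1 may not be meant to count as enrolled. These points bear on how large the loss will be. They do not support zero loss, which is what the 100-patient figure requires.

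The mixed model in 7.3.1 uses partly observed patients and may lose less power. That stands, but 7.2 powers a two-sample t-test and gives no correlation from which the model's power could be computed. A patient with no post-discharge score adds little under either method.

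Finally, this is called a feasibility study. It nevertheless lists quality-of-life impact as a primary objective (2.1.1) and attaches a specific power claim to it.

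**Conclusion.** The concern holds. The 80% at 100 patients is correct only with complete scores from all 50 per arm. With an assumed 20% loss at a single time point, power for 11.467 points is 72%, and the difference detectable with 80% power is 12.8 points; over 10-30% loss the ranges are 76-67% and 12.1-13.7 points. For the 10-point difference on which the trial was first sized, 100 enrolled gives 70% even with complete data. At 140 enrolled, power for 10 points is 79-69% over the same loss range.

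These results rest on SD 22.9, equal loss in both arms, a one-sided 0.05 t-test at one time point, and loss rates that the documents do not supply. They do not describe the mixed model.

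**What to change.** Restate 7.2 on evaluable patients. Give an assumed range of loss at a single Aim 1 time point, for example 10-30%, and the resulting power and 80%-power difference at 100 and at 140 enrolled, as in the table above. Say that these figures apply to the single-time-point t-test and that the mixed model may lose less. Say whether patients excluded under 3.2.1 count toward the 100-140.

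A minor clarification: repeat the one-sided 0.05 level in 7.3.1. If testing will be two-sided, restate power; with no loss it is about 70% at 50 per arm for 11.467 points and 73% at 70 per arm for 10 points.

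The cost is a rewording of 7.2 and one clause in 7.3.1. Enrolment, design and analysis stay as they are. The stated figures become less favourable.

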7.3 Data Analysis Plans

7.3.1 Aim 1: Impact of PRO monitoring with symptom alerts, compared to PRO monitoring without alerts, after thoracic surgery on post-operative quality of life.

Impact will be determined by comparing baseline quality of life to quality of life at the following timepoints: Day 14, Day 60, Day 120, Day 180, and Day 365 post-discharge. QOL will be measured by administering European Organisation for Research and Treatment of Cancer's (EORTC) EORTC QLQ-LC13 and EORTC QLQ-C30. These surveys will be scored according to methods described in the EORTC scoring manual: <https://qol.eortc.org/manual/scoring-manual>.

Student's T and/or Wilcoxon rank sum tests will be used to perform bivariable comparisons of EORTC scores at each of the time points (baseline/pre-operative and Day 12, Day 60, Day 120, Day 180, and Day 365 post-operative).

Additionally, a linear mixed effect model will be used to assess the average

change in EORTC scores over time amongst both groups, and the difference in average trajectory between them, after accounting for repeated measures and within- and between- subject variability. Both a random intercept and slope (for time) statement will be used, and an unstructured correlation matrix will be applied. The random intercept and slope will allow us to assess the impact of symptom alerts while allowing for random variation in baseline quality of life and trajectories.

If there are convergence issues, simpler correlation structures may be used (e.g. independent) or the random slope parameter may be dropped. Dropping the random slope parameter will mean we are assuming that there is no/minimal individual variation in trajectory across patients.

7.3.2 Aim 2: Determine feasibility of 3-month post-operative PRO symptom monitoring with alerts.

The proportion of completed symptom surveys (overall and in each arm) at 3-months postoperative will be calculated, as well as the proportion of participants who completed all surveys during that time. Chi-square, Student's T, and Wilcoxon rank sum tests will be used to compare patient demographics, study arm, and surgery characteristics between those who did and did not complete all surveys to attempt to identify predictors of compliance. Multivariable logistic regression may also be used.

Similar methods will be used to assess proportion of symptom alerts that generate a clinician response.

7.3.3 Aim 3: Identify barriers/facilitators of PRO monitoring through semi-structured interviews.

Patient and caregiver interview transcripts will be analyzed as they are collected. Transcripts will be coded using in vivo coding methods and a code book will be created. Interviews will continue until thematic saturation is achieved, which will be defined by no new codes being generated to add to the code book.

7.3.4 Sub-Aim 1: Impact of PRO monitoring with symptom alerts, compared to PRO monitoring without symptom alerts, on post-operative readmission and mortality rates.

Kaplan Meier curves and Cox proportional hazards regression will be used to assess the impact of study treatment arm on 30-day and 90-day emergency department (ED) visits, readmissions, and all-cause mortality, as well as 1-year all-cause mortality. A linear mixed effect model will be used to assess the change in 2-year quality of life (described in Aim 1).

Patients who are lost to follow-up will be censored at their last clinician/study interaction. Mortality will be treated as a competing risk for ED visits and readmission. This aim will be approached as an intent-to-treat analysis and will not require that patients used their PRO monitoring or had symptom alerts sent to

their clinician.

7.3.5 Sub-Aim 2: Determine the feasibility of PRO monitoring for assessing quality of life.

Similar methods to Aim 2 will be used. The proportion of completed QOL surveys (overall and in each arm) at each time point (baseline/pre-operative and 2-weeks, 6-months, 1-year, and 2-year post-operative) will be calculated, as well as the proportion of participants who completed all surveys during that time. Chi-square, Student's T, and Wilcoxon rank sum tests will be used to compare patient demographics, study arm, and surgery characteristics between those who did and did not complete all surveys to attempt to identify predictors of compliance. Multivariable logistic regression may also be used.

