1.2 Background

Patient-centered outcomes after surgery go beyond traditionally measured morbidity and mortality to include QOL [11]. Patients undergoing thoracic surgery strongly value communication from their providers about anticipated physical functioning post-operatively [12, 13]. Patients who require thoracic surgery are older, have comorbidities, and have greater decreases in QOL after often morbid treatments compared to other patients [14]. Therefore, 90-day readmissions after thoracic surgery remain high at 18%, largely due to symptomatic adverse events including post-operative complications and new cardiopulmonary diagnoses [4, 15]. While symptom severity and physical functioning worsen for up to 6 months after thoracic surgery [16-18], pain and QOL do return to baseline by 12 months [19], suggesting a window in the first year after surgery during which PROs can be better monitored and managed.

In non-surgical populations, management of patient-reported symptoms has been extensively linked to improvements in care delivery including readmissions. The NIH has developed a PRO version of the Common Terminology Criteria for Adverse Events (PRO-CTCAE), which is a validated library assessing the presence, frequency, severity, and interference with usual activities of symptoms. Responses are provided by patients on a 5-point Likert scale with recall being over the prior week [20]. PRO-CTCAE is feasible for use in a variety of patient populations [21]. In surgical patients, PROs have been used as clinical outcomes, for quality improvement, and as outcomes in comparative effectiveness research [22]. In thoracic surgery patients specifically, PRO assessment through weekly

telephone surveys has demonstrated symptom improvement; however, items assessed were standard cancer-related and one surgical specific symptom. Further, only 60% of symptom alerts lead to intervention by clinicians [8].

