2.0 STUDY OBJECTIVES AND ENDPOINTS

2.1 Primary Objectives

2.1.1 To determine impact of PRO monitoring with symptom alerts compared to PRO monitoring without symptom alerts after thoracic surgery on post-operative quality of life.

2.1.2 To determine feasibility of 90-day post-operative PRO symptom monitoring after thoracic surgery symptom monitoring eliciting a clinician response.

Feasibility is defined as:

1. $\geq 50\%$ of participants complete all symptom surveys until 3 months post-operatively
2. $\geq 50\%$ of symptom alerts generate a clinician response

2.1.3 To determine barriers/facilitators of PRO monitoring after thoracic surgery through semi-structured interviews of patients and caregivers.

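### Section 7.3.1 defines the impact of alerts as baseline versus later quality of life without mentioning the arms, and names no deciding between-arm contrast

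*Combined protocol and SAP*

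**What the plan says.** Objective 2.1.1 is a comparison of arms: "To determine impact of PRO monitoring with symptom alerts compared to PRO monitoring without symptom alerts after thoracic surgery on post-operative quality of life". The heading of section 7.3.1 repeats it: "Aim 1: Impact of PRO monitoring with symptom alerts, compared to PRO monitoring without alerts, after thoracic surgery on post-operative quality of life".

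The first sentence under that heading sets a different comparison: "Impact will be determined by comparing baseline quality of life to quality of life at the following timepoints". It then lists Days 14, 60, 120, 180 and 365 after discharge.

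Two analyses follow:
- Per-visit tests: "Student's T and/or Wilcoxon rank sum tests will be used to perform bivariable comparisons of EORTC scores at each of the time points". The visits include baseline. No grouping variable is given.
- A longitudinal mixed model, brought in as an addition to those tests. Its two targets are given as: "change in EORTC scores over time amongst both groups, and the difference in average trajectory between them". The same paragraph says that the random effects let the team assess the impact of alerts.

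Section 7.2 sizes the trial with a two-group t-test at a one-sided 5% level: 66 per arm for a 10-point difference with SD 22.9.

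**The concern.** The null hypothesis of objective 2.1.1 is that the arms do not differ. The null of the opening sentence in 7.3.1 is that quality of life has not changed since before surgery. The protocol gives reason to expect change in both arms. Section 1.2 says "symptom severity and physical functioning worsen for up to 6 months after thoracic surgery", and section 1.3 calls declines in quality of life common.

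A pre/post comparison picks up the course of recovery, which both arms share. If it were run within each arm, significance in one arm and not in the other could be taken for an alert effect although the arms are equal. The one-sided 5% error rate in section 7.2 belongs to a between-arm test and would not carry over.

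The later paragraphs do not settle which result decides. The t/Wilcoxon sentence does not name the arms, although section 7.3.4 does so for its own outcomes. The mixed model is introduced as an addition and yields both the average change over time and the difference between groups. An analyst could report within-arm change as the primary result and still claim to have followed 7.3.1.

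**Working it through.** **1. The plan's own figure.** Inputs from section 7.2: difference 10, SD 22.9, one-sided alpha 0.05, two-group t-test. The noncentrality is difference / (SD × √(2/n)). Exact noncentral-t power is 79.7% at 65 per arm and 80.2% at 66, so 66 is reproduced. With 50 per arm and a difference of 11.467, power is 80.0%, also as stated. The trial is sized for a between-arm test.

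**2. The opening sentence used as the deciding test, with no alert effect.** The documents give neither the size of the post-operative decline in EORTC points nor the correlation between baseline and follow-up. I assume a common decline of 0, 5 or 10 points, a correlation r of 0.3 to 0.7, and SD 22.9 at both times. Section 7.3.1 states no sidedness; I use two-sided 0.05.

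SD of change = 22.9 × √(2(1 − r)), which is 27.1, 22.9 and 17.7 for r = 0.3, 0.5 and 0.7.
Noncentrality = decline × √n / SD of change. Example: n = 70, r = 0.5, decline 10 gives 10 × 8.367 / 22.9 = 3.65, and a rejection rate of 95%.

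| Paired test on | Decline 0 | Decline 5 | Decline 10 |
|---|---|---|---|
| One arm of 50 | 5% | 25–50% | 73–97% |
| One arm of 70 | 5% | 33–64% | 86–99.6% |
| Both arms pooled, 140 | 5% | 58–91% | 99% or more |

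Each range runs from r = 0.3 to r = 0.7. In one arm of 70, rejection passes 50% only when the decline exceeds about 4.2 points (r = 0.7) to 6.4 points (r = 0.3).

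**3. Significant in exactly one of two identical arms.** With rejection rate p per arm this is 2p(1 − p). At 70 per arm and a 5-point decline, p = 0.33, 0.44 and 0.64 give 44%, 49% and 46%.

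**4. Between-arm tests on the same data.** In 6,000 simulated trials per setting, two-sample t-tests on follow-up scores or on change scores rejected in about 4–6% at every decline and correlation tried.

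**5. What the unadjusted per-visit tests give up.** Adjusting for baseline reduces the residual SD to 22.9 × √(1 − r²), which is 21.8, 19.8 and 16.4. With 50 per arm, a 10-point difference and one-sided 0.05, power is 70.0% unadjusted. Adjusted, it is 73.5%, 80.5% and 91.8% for r = 0.3, 0.5 and 0.7.

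**The case against.** The strongest reply is that the opening sentence only names the outcome, change from baseline, and its visits, and that the rest of the plan supplies the comparison of arms. No paired or signed-rank test appears anywhere. The rank-sum test is an independent-samples test, and a test run at baseline cannot be a comparison of baseline with later scores. The mixed model estimates a difference in trajectory between groups and is tied in the text to the impact of alerts. The heading, the objective and the sample size are all between-arm.

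Most of this stands. It shows what the authors very probably intend, and it means that the paired-test rates in the working are not error rates of the trial as planned. The quotation from section 1.2 also needs its context: it concerns symptoms and physical function, and the same sentence expects quality of life to return to baseline by 12 months. At Day 365 even the literal test would then reject only about 5% of the time.

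It could also be said that baseline adjustment goes beyond clarification. That is fair as a description. But the baseline score is already collected, and if the opening sentence is about change from baseline, the per-visit tests on raw scores do not deliver it.

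What the reply does not remove is that the one sentence stating how impact is to be determined leaves out the arms, and that nothing else in 7.3.1 is named as the deciding contrast.

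**Conclusion.** The point holds as a conflict within the plan and a gap in pre-specification. The stated rule for impact does not match the randomised question. The analyses that do match it are not identified as deciding, and the per-visit ones ignore baseline.

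A reader might infer that the trial will usually report an impact when alerts do nothing. The documents do not support that. The planned model compares arms, the t/Wilcoxon tests are most naturally read the same way, and between-arm tests hold about 5%. The high rates apply only if the opening sentence were used as the deciding test. They also rest on an assumed decline, an assumed correlation and a two-sided test. With a 5-point decline in one arm of 70, rejection exceeds half only towards the upper end of the correlations tried. A one-sided test for improvement would reject less than 5% of the time under a decline, so even the direction of the error depends on a choice that 7.3.1 does not state.

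The sample size is unaffected. The possible gain in power from baseline adjustment, about 4 to 22 percentage points at 50 per arm, likewise depends on the assumed correlation.

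**What to change.** Replace the opening sentence of 7.3.1 with wording such as:

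> *The impact of alerts will be judged by the difference between the active and passive arms in EORTC score at Days 14, 60, 120, 180 and 365 after discharge, adjusted for the baseline score. Within-arm changes from baseline are descriptive only.*

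In the t/Wilcoxon sentence, add that the comparisons are *between the two arms*. That sentence also lists Day 12 where the one before it lists Day 14; the two should be reconciled in the same edit. The replacement wording still covers five visits and does not choose a scale, so the sponsor should also state which contrast decides and whether the mixed model or a per-visit comparison supplies it.

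The cost is a few sentences of analysis wording. The only downside is that within-arm improvement or decline can no longer be cited as evidence about alerts.
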